3 STUDY IMPLEMENTATION

3.1 STUDY DESIGN

This is a prospective, randomized, single-blinded, controlled trial in patients with a suspicious or confirmed PTC ≤ 4 cm without clinical evidence of lymphadenopathy or extrathyroidal extension on imaging. Preoperative evaluation will be performed to establish the baseline status of participant's QOL, neck pain (scale 1 to 10), subjective voice and objective vocal cord function, and swallowing status using standardized questionnaires (see below). *BRAF* V600E mutation status of the tumor will be assessed in all patients after thyroidectomy. Enrolled participants will be randomly assigned preoperatively to receive either TT alone or TT with pCND. Participants and their families will be blinded from the results of randomization. If a patient who is assigned to TT alone group is found to have LNM intraoperatively by frozen section, a CND will be performed and the patient will remain in TT alone group (intention to treat). Participants in both groups will receive uniform, routine postoperative care and follow-up evaluation per protocol (see below). Stim-Tg will be measured in all participants prior to remnant ablation at 3 months postoperatively (prior to remnant ablation, if indicated). Stim-Tg at 1-year post-remnant ablation or 1 year postoperatively if participants do not receive remnant ablation will be performed in patients enrolled at the NIH but is optional in patients enrolled at non-NIH site(s). Tg and anti-thyroglobulin antibodies will be measured annually for 10 years. The postoperative complications and QOL of participants will be assessed during preoperative evaluation, postoperative day 1, 2 weeks, 3 and 6 months, 1, 5 and 10 years postoperatively. Surgical outcome will be evaluated at postoperative day 1, 2 weeks, and 6 months postoperatively. Participants will have an evaluation for radioactive iodine ablation by the

Abbreviated Title: Prophylactic Central Neck Dissection

Version Date: 01/15/2019

endocrinology service. The standardized protocol will be used based on histologic findings and patient's risk of recurrence per NIDDK protocol. (**Table 2**) Similarly, participants will be managed using a standardized protocol for TSH suppression therapy based on the risk of recurrence.

Table 2. Post-operative risk stratification: Guideline for management of patients with clinical characteristics that modify initial assessment of risk¹

Clinical factor	Postoperative Stim-Tg (ng/ml)	^{131}I ablation/preparation²	Thyroid hormone goal
T1-T2, Nx or N0	<5	No remnant ablation	TSH low normal ³
T1-T2, Nx or N0	≥5	30 mci(91)/WD or rhTSH	TSH low normal
T3, Nx or N0 ≤45 years old	<5	No remnant ablation	TSH subnormal ⁴
	≥5	50-100 mCi/ WD or rhTSH	TSH subnormal
T3, Nx or N0 ≥45 years old	<5	No remnant ablation	TSH subnormal
	≥5	100 mCi/ WD or rhTSH	TSH subnormal
T4, Any N	Any	150 mCi/WD	TSH suppressed ⁵
N1 <45 years old	<5	No remnant ablation	TSH subnormal
	≥5	50-100 mCi/ WD or rhTSH	TSH subnormal
≥45 years old	<5	No remnant ablation	TSH suppressed

Abbreviated Title: Prophylactic Central Neck Dissection

Version Date: 01/15/2019

Clinical factor	Postoperative Stim-Tg (ng/ml)	¹³¹ I ablation/preparation ²	Thyroid hormone goal
	≥5	100 mCi/ WD or rhTSH	TSH suppressed
M1	Any	≥ 150 mCi/WD	TSH suppressed
Histologic variants			
Tall cell			
Diffuse Sclerosing			
Hurthle	Any	≥ 150 mCi/WD	TSH suppressed
Insular			
Anaplastic/ Dedifferentiated			

WD: withdrawal of thyroid hormone; rhTSH; recombinant human TSH

¹The management may vary individually based on patient's risk factors and investigator's discretion

² All follow 2-week low iodine diet

³ Low normal goal: TSH 0.5 to 1 mU/L

⁴ Subnormal goal: TSH 0.1 to 0.5 mU/L

⁵ Suppressed goal: TSH <0.1 mU/L

Biochemical cure or remission in this study is defined as stim-Tg < 2 ng/ml or unstimulated Tg \leq 0.2 ng/ml. Biochemical persistent or recurrent disease is suspected when stim-Tg \geq 5 ng/ml or unstimulated Tg $>$ 0.3 ng/ml or a conversion or a rise in anti-Tg antibodies.

An interim analysis will be performed after 90 who do not have anti-thyroglobulin antibody patients are enrolled (See Section 7), including a subgroup analysis based on *BRAF* V600E mutation status.

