1. INTRODUCTION

1.1 STUDY OBJECTIVES

1.1.1 Primary Objective:

- To determine biochemical cure rates in patients with low-risk PTCs undergoing total thyroidectomy (TT) with and without pCND as measured by postoperative TSH-stimulated serum thyroglobulin (stim-Tg) at 3 months (prior to RAI treatment).

1.1.2 Secondary Objectives:

- To determine biochemical cure rates in patients with low-risk PTCs undergoing total thyroidectomy (TT) with and without pCND as measured by postoperative TSH-stimulated serum thyroglobulin (stim-Tg) at 1 year postoperatively in patients who will not receive RAI or 1 year post remnant ablation.
- To determine the following outcome measures in patients undergoing TT with and without pCND:
 - a. The QOL of patients with low-risk PTCs undergoing TT and pCND to those undergoing TT alone using the SF-36v2 standardized questionnaire (preoperative, postoperative day 1, 2 weeks, 3 and 6 months, 1, 5 and 10 years postoperatively).
 - b. Neck pain (preoperative, postoperative day 1, 2 weeks, and 6 months postoperatively).
 - c. Subjective voice quality, swallowing impairment (preoperative, postoperative day 1, 2 weeks, and 6 months postoperatively) as well as objective vocal cord dysfunction (preoperative and postoperative day 1 and 6 months postoperatively only if abnormality is found on postoperative day 1) and requirement for intervention.
 - d. Rate and duration of both symptomatic and asymptomatic hypoparathyroidism including requirement and duration of postoperative oral or IV calcium replacement as well as vitamin D analogue for hypoparathyroidism (preoperative PTH, postoperative day 1, 2 weeks and 6 months postoperatively).
 - e. Rate of cervical wound complications (hematoma, seroma, and surgical site infection) and intervention(s) required.
 - f. The use of radioactive iodine.
 - g. Oncologic outcome:
 - I. Radiographic evidence with biopsy or pathology proven recurrent disease.
 - II. Thyroid cancer-related death.
 - h. The impact of BRAF V600E mutation status on lymph node metastasis in patients with low-risk PTC undergoing TT with or without pCND. In addition, we will compare the rate of disease recurrence in patients undergoing pCND to those who will not undergo pCND, by BRAF V600E mutation status.

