Based on the studies cited above, stim-Tg <2 ng/ml and unstimulated Tg ≤ 0.2 ng/ml have been associated with biochemical cure or remission in patients with differentiated thyroid cancer and stim-Tg <2 ng/ml will be used in this protocol as a cut-off for biochemical cure. Stim-Tg >5 ng/ml or unstimulated Tg >0.3 ng/ml has been associated with persistent and recurrent disease([11](#), [48](#), [75](#), [76](#)), and therefore, will be used in this protocol as a cut-off for biochemical persistent/recurrent disease.

Serum Tg is used to guide postoperative radioiodine therapy, level of TSH suppression and the extent of surveillance for recurrent/persistent disease([77](#)).

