7 STATISTICAL CONSIDERATIONS

The primary goal of this study is to determine if there is a difference in biochemical cure rates based on postoperative stimulated thyroglobulin levels (stim-Tg) at 3 months, primarily focusing on the rates of athyroglobulinemia, in patients with clinically node negative PTC undergoing TT and with and without pCND. Serum Tg, especially when TSH-stimulated, is a very sensitive and specific marker for residual thyroid tissue, persistent or recurrent differentiated thyroid cancer of follicular cell origin, in the absence of anti-Tg antibodies. Because patients with differentiated thyroid cancer whose Tg and/or stim-Tg becomes undetectable after treatment(s) are typically considered free of disease in the absence of radiographic evidence of tumor, we use athyroglobulinemia as a surrogate for biochemical remission. We conservatively estimate that there should be at least a 20% higher rate of athyroglobulinemia in patients undergoing TT and pCND ($\theta_2 = 0.4$) compared to TT alone ($\theta_1 = 0.2$) during early postoperative period. With a total of 180 evaluable participants (approximately n=90 for each arm) who have no anti-thyroglobulin

Abbreviated Title: Prophylactic Central Neck Dissection

Version Date: 01/15/2019

antibody, the trial will have 80% power ($\beta=0.20$) to detect the difference between 0.2 and 0.4 using a Fisher's exact test with two-sided significance level (α) of 0.05.

The protocol will not have any stratification at the time of randomization because there are no known factors associated with athyroglobulinemia. Because this study only enrolls patients with low-risk PTC, it is unlikely that there would be many patients with advanced age and advanced PTC that may be unevenly distributed which may confound with the results of the study.

This study will be monitored by the NCI/CCR Data Safety and Monitoring Board, both for toxicity as well as efficacy and futility with respect to the primary endpoint.

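### The term in the primary objective, biochemical cure, is defined as stim-Tg below 2 ng/ml, but Section 7 sizes, tests and monitors athyroglobulinemia with no numeric limit

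*Combined protocol and SAP*

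**What the plan says.** **Objective.** The Précis and 1.1.1 set the primary objective as the biochemical cure rate with and without prophylactic central neck dissection (pCND), on stim-Tg at 3 months before radioiodine. Neither gives a threshold.

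**Definition of the term.** Section 1.2.2.5 states that "stim-Tg <2 ng/ml will be used in this protocol as a cut-off for biochemical cure". Section 3.1, after Table 2, states "Biochemical cure or remission in this study is defined as stim-Tg < 2 ng/ml or unstimulated Tg" at or below 0.2 ng/ml. The next paragraph of 3.1 refers the interim analysis to Section 7.

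**Statistical section.** Section 7 opens with the same goal, to "determine if there is a difference in biochemical cure rates based on postoperative stimulated thyroglobulin levels" at 3 months, but continues "primarily focusing on the rates of athyroglobulinemia". It justifies this by reference to patients "whose Tg and/or stim-Tg becomes undetectable after treatment(s"), and concludes that "we use athyroglobulinemia as a surrogate for biochemical remission". The sample size, 180 evaluable patients, gives 80% power "to detect the difference between 0.2 and 0.4" with Fisher's exact test at two-sided 0.05. Both rates are for athyroglobulinemia. The interim efficacy rule and the futility rule are stated for the same variable. Section 7 contains no limit in ng/ml and does not mention the 2 ng/ml cut-off.

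**Only figure for undetectable.** Section 1.2.2.5 puts undetectable stim-Tg at below 0.5 ng/mL when summarising the literature. No section adopts it for the trial.

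**The concern.** The objective uses a term that the protocol defines in one way, and the statistical section then tests something narrower. Calling athyroglobulinemia a surrogate connects the two terms but does not make them equal. They differ on patients with low but detectable stim-Tg, a group whose clinical significance 1.2.2.5 itself calls unclear.

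Two things follow. First, a biochemical cure rate reported by the 3.1 definition would be an endpoint that was neither sized nor monitored, and it could lead to a different conclusion from the Section 7 test on the same data. Second, even if Section 7 governs, its endpoint cannot be applied uniformly as written. It has no numeric limit, the and/or wording leaves open whether stimulated or unstimulated Tg counts, and the trial includes non-NIH sites.

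**Working it through.** **1. The definitions side by side**

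| 3-month stim-Tg | 1.2.2.5 and 3.1 | Section 7 |
|---|---|---|
| Undetectable | cured | success |
| Detectable, below 2 ng/ml | cured | failure |
| 2 ng/ml or above | not cured on this limb | failure |

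The unstimulated limb appears only in 3.1 and can only add cures, so it widens the gap. It is left out of the calculations below.

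**2. The plan's own figure**

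Inputs from Section 7: n = 90 per arm, rates 0.2 and 0.4, two-sided Fisher's exact test, alpha 0.05.

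Power = sum over x, y of Bin(x; 90, p1) × Bin(y; 90, p2) × 1{Fisher p(x, y) < 0.05}

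- p1 = 0.2, p2 = 0.4: **80.2%** (89 per arm gives 79.6%). The stated power is reproduced.
- Actual size with 0.2 in both arms: 3.2%.
- Ceiling: 180 / (1 − 0.20) = 225, as stated.

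There is no sample-size error for athyroglobulinemia.

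**3. The same 90 per arm on stim-Tg below 2 ng/ml (assumed rates)**

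The documents give no rates by arm for this definition. Let c be the assumed TT-alone rate and f the share of the 20-point effect that crosses 2 ng/ml, so the pCND rate is c + 0.20f. Undetectable patients are also below 2 ng/ml, so c ≥ 0.2 and c + 0.20f ≥ 0.4, which gives c ≥ 0.4 − 0.20f. Grid steps are 0.05.

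| Share crossing | Range of c | Exact power on <2 | Athyroglobulinemia significant, <2 not | Reverse |
|---|---|---|---|---|
| None (f = 0) | 0.40-0.80 | 3.1-3.7% | about 78% | about 1-2% |
| Half (f = 0.5) | 0.30-0.80 | 21-40% | about 46-60% | 0-5% |
| All (f = 1) | 0.20-0.75 | 71-97% | 0-16% | 0-19% |

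The last two columns come from simulation, 1,000,000 trials per case. Each patient is undetectable with probability a (0.2 or 0.4 by arm), detectable but below 2 with probability (arm's <2 rate − a), and otherwise at or above 2.

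- In the all-crosses row, power is 80.2% at c = 0.20, where the two endpoints coincide. It is 70.7% at 0.40, 80.2% again at 0.60 and 96.8% at 0.75.
- The effect on <2 could also exceed 20 points, so none of these figures is a bound.
- The nearest rate in the documents is 56% at or below 1 ng/ml, in a microcarcinoma cohort of 80, of whom 11 had a central neck dissection (1.2.2.5). The population and cut-off both differ. Taking c = 0.56 purely as an assumption, power is 77.3% for a 20-point effect and 23.9% for a 10-point effect.

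**4. False-positive cost of choosing either definition**

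With athyroglobulinemia at 0.20 in both arms, the probability that at least one definition is significant, by common rate for <2:

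| Rate for <2 | 0.25 | 0.30 | 0.40 | 0.50 | 0.60 | 0.70 | 0.80 |
|---|---|---|---|---|---|---|---|
| Either significant | 5.0% | 5.5% | 6.1% | 5.9% | 6.5% | 6.4% | 6.3% |

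The Section 7 endpoint alone gives 3.2%.

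**The case against.** The best defence is that the tested variable is not in doubt. Section 7 names athyroglobulinemia, gives a reason, says that the monitoring board looks at efficacy and futility for the primary endpoint, and then applies both rules to athyroglobulinemia only. No analysis of stim-Tg below 2 ng/ml is specified anywhere. Table 1 in 1.2.2.2 lists a higher rate of athyroglobulinemia as a result under biochemical cure, so the choice fits the stated rationale. The sentence in 3.1 follows a management table and is paired with a definition of suspected persistent or recurrent disease, so it can be read as classifying patient status. A candidate limit, below 0.5 ng/mL, already appears in 1.2.2.5.

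Much of this stands. A reader might infer that the primary test is undecided or the trial undersized; Section 7 supports neither. The status reading of 3.1 does not remove the conflict, because 1.2.2.5 adopts the 2 ng/ml cut-off for biochemical cure in this protocol and that is the objective's own term. The 0.5 figure describes cited literature and is not adopted.

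A reader might also infer that the limit will be chosen with results by arm in view. Section 3.1 states blinding only for participants and their families, but 6.4.2 withholds interim outcome results from investigators and nothing in the documents points to such a choice. That is conjecture, and for these two definitions the false-positive gain is small. The effect of choosing among different limits for undetectable was not quantified.

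**Conclusion.** The plan is wrong as written on one point: the term in the primary objective has a definition that contradicts the variable sized, tested and monitored, and that variable lacks a numeric limit. This should be fixed, but it is an unaligned endpoint definition and not a flaw in the sample-size calculation.

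The 80% power belongs to athyroglobulinemia at 0.2 against 0.4 and cannot be quoted for stim-Tg below 2 ng/ml. How far power on that definition departs from 80% is unknown. The range from about 3% to 97% rests wholly on assumed rates; it shows that power does not transfer automatically, not that it is lost. The 3% end assumes that pCND has no effect at all on the proportion below 2 ng/ml. The firm conclusion is narrower: the two definitions count some patients differently and can give different conclusions from the same data.

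**What to change.** 1. In the Précis, 1.1.1, 1.2.2.5, 3.1 and Section 7, name one primary endpoint: athyroglobulinemia on stimulated Tg at 3 months, before radioiodine. Remove the and/or wording that admits unstimulated Tg.
2. Give it one numeric limit, used at all sites and for the interim, futility and final tests. The figure of below 0.5 ng/mL in 1.2.2.5 is a candidate. Confirm that the 0.2 and 0.4 rates refer to the chosen limit; if not, restate the rates and the power.
3. Make stim-Tg below 2 ng/ml a named secondary endpoint, and say which definition the 1-year biochemical cure objective in 1.1.2 uses.
4. Have the limit set by people without sight of outcomes by arm, and record this in the amendment.

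The cost is wording in five places plus a check of the assumed rates. The sponsor gives up the choice of definition, and the power statement may need revision if the rates do not match the limit. Aligning on 2 ng/ml instead would cost more, because it needs new assumed rates, a new power statement and restated interim and futility rules. Neither route requires a change to patient management.

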1.2.2.5 Serum thyroglobulin and postoperative surveillance

An undetectable stim-Tg (< 0.5 ng/mL) in the absence of anti-Tg antibody has an approximately 98–99.5% likelihood of identifying patients completely free of tumor on follow-up(55, 56). Detectable Tg after RAI ablation is associated with higher rate of disease recurrence (**Figure 2A**) (57). In addition, Tg level is typically higher in patients with distant metastasis and is correlated with tumor burden. (58, 59) However, stim-Tg may fail to identify patients with clinically significant tumor burden in the presence of anti-Tg antibody or in patients with poorly differentiated or other aggressive thyroid cancer subtypes, due to low Tg expression. Approximately 20% of patients who have no clinical evidence of disease with serum Tg levels < 1 ng/mL during thyroid hormone suppression of TSH (60) will have a serum Tg level > 2 ng/mL after rhTSH stimulation or thyroid hormone withdrawal at 12 months after initial therapy with surgery and RAI. In this patient population, one third will have identification of persistent or recurrent disease and of increasing Tg levels, and the other two thirds will remain free of clinical disease and will have stable or decreasing stim-Tg levels over time (61). Using a current highly sensitive Tg assay, undetectable unstimulated Tg (≤ 0.1 ng/ml) has a very high negative predictive value to identify patients without evidence of disease when stim-Tg is used as a benchmark(62, 63).

Figure 2. Serum thyroglobulin and outcomes of thyroid cancer: **A:** detectable post-ablative Tg is associated with higher recurrent rate; **B:** Disease-free survival in patients with stim-Tg levels ≤ 20 pmol/L and >20 pmol/L, 3 months after total thyroidectomy for well-differentiated thyroid cancer (1 ng/ml of thyroglobulin= ~ 1.515 pmol/L).

Abbreviated Title: Prophylactic Central Neck Dissection
Version Date: 01/15/2019

[figure not shown]
Figure 2

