3.3.1.3 Three months postoperatively (\pm 2 weeks)

- To assess the primary endpoint of the study, all participants will be seen in clinic, and will either receive recombinant TSH injections or start thyroid hormone withdrawal.
- Participants will be evaluated by endocrinology service for stim-Tg measurement and DxWBS per standardized protocol (optional in patients enrolled at non-NIH site):

Abbreviated Title: Prophylactic Central Neck Dissection

Version Date: 01/15/2019

- a. Laboratory evaluation includes: (stimulated) Tg, anti-thyroglobulin antibodies, TSH, FT4, T3, Calcium total, Ionized Calcium, Magnesium total (Mg), Inorganic Phosphorus, and intact PTH.
- b. DxWBS or RAI with post therapy scan will be performed as needed. If DxWBS is indicated patients should start and maintain a low iodine diet two weeks prior to the scan.
- c. Baseline neck USG.
- d. QOL using SF-36 v2 questionnaire

3.3.1.4 Six months postoperatively (\pm 2 weeks), participants will be seen in clinic and will

- a. Fill out the following questionnaires.
 - QOL using SF-36 v2 questionnaire
 - Neck pain (scale 0 (no pain) to 10 (unimaginable, unspeakable pain))
 - Voice quality using Voice Handicap Index-10 questionnaire
 - Swallowing symptoms using Swallowing Impairment Score (SIS-6) questionnaire
- b. Undergo flexible laryngoscopy only if there were impaired vocal cord function(s) on postoperative day 1 or 2.
- c. Receive laboratory evaluation which includes CBC with differential, Sodium (Na), Potassium (K), Chloride (Cl), Total CO₂ (bicarbonate), Creatinine, Glucose, Urea nitrogen (BUN), Albumin, Calcium total, Ionized Calcium, Magnesium total (Mg), Inorganic Phosphorus, TSH, FT4, T3, Tg, anti-thyroglobulin antibodies, and intact PTH.
- d. Undergo soft tissue neck USG. Any suspicious lymph node(s) or lesion(s) will be biopsied for cytology and Tg wash.

3.3.1.5 One year postoperatively (\pm 2 weeks) for participants who do not receive remnant ablation **or one year post-remnant ablation**, they will be seen in clinic and

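### Section 3.1 lets an unstimulated thyroglobulin establish biochemical cure, against the objectives and Section 1.2.2.5, so the 1-year cure rate could rest on different tests at different sites

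*Combined protocol and SAP*

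**What the plan says.** Three places in the combined protocol and SAP bear on what counts as biochemical cure.

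- **Section 3.1, text after Table 2.** "Biochemical cure or remission in this study is defined as stim-Tg < 2 ng/ml or unstimulated Tg" at or below 0.2 ng/ml. The next sentence begins "Biochemical persistent or recurrent disease is suspected when stim-Tg" and sets the limit at 5 ng/ml or more, or an unstimulated Tg above "0.3 ng/ml or a conversion or a rise in anti-Tg antibodies". The text does not say which test prevails when the two disagree.
- **Section 1.2.2.5.** This section notes that unstimulated Tg of 0.2 ng/ml or less has been associated with cure, but for the protocol's own rule it names only the stimulated value: "stim-Tg <2 ng/ml will be used in this protocol as a cut-off for biochemical cure".
- **Section 1.1.** The primary objective is a cure rate "as measured by postoperative TSH-stimulated serum thyroglobulin (stim-Tg) at 3 months (prior to RAI treatment". The first secondary objective is again a stim-Tg cure rate, at 1 year after surgery or 1 year after remnant ablation.

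On which tests are done: Section 3.1 has stim-Tg measured in every participant at 3 months, and the laboratory list for that visit in 3.3.1.3 reads "Laboratory evaluation includes: (stimulated) Tg, anti-thyroglobulin antibodies, TSH, FT4, T3". At 1 year, the Précis, Section 3.1 and Section 3.3.1.5 make stim-Tg part of follow-up for NIH patients and optional elsewhere. The Précis also has unstimulated Tg checked annually for 10 years.

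**The concern.** Section 3.1 is the only place where an unstimulated value can establish cure by itself. The objectives and Section 1.2.2.5 rest cure on the stimulated value. An analyst who programs the endpoint from 3.1 and one who programs it from 1.1 and 1.2.2.5 would classify some patients differently, and nothing in Section 7 settles which is right. This is a conflict between stated rules, not a missing detail.

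The 1-year secondary cure rate is at stake. If the 3.1 wording is applied, an NIH patient is judged on a stimulated test, while a non-NIH patient without one is judged on an unstimulated test under the same label. The reported rate would then partly reflect where patients were followed. The definition could also end up being chosen after the data are seen.

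**Working it through.** **The plan's own figure.** Section 7 gives 180 evaluable participants (about 90 per arm), rates of 0.2 and 0.4, Fisher's exact test, two-sided 0.05, and 80% power. Exact enumeration at 90 per arm gives 80.2%, so the figure reproduces. The accrual ceiling also follows: 180 / (1 − 0.20) = 225. Both rest on athyroglobulinemia, not on the Section 3.1 cure definition, so neither changes here.

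**Applying the rules to pairs of values (ng/ml).** Section 3.1 cure: stim < 2 or unstim ≤ 0.2. Section 3.1 suspected persistence, Tg criteria only: stim ≥ 5 or unstim > 0.3. Section 1.2.2.5 cure: stim < 2.

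| stim-Tg | unstim. Tg | 3.1 cure | 3.1 suspected persistence | 1.2.2.5 cure |
|---|---|---|---|---|
| 1 | 0.1 | yes | no | yes |
| 1 | 0.5 | yes | yes | yes |
| 3 | 0.1 | yes | no | **no** |
| 3 | 0.25 | no | no | no |
| 6 | 0.1 | yes | yes | **no** |
| 6 | 0.5 | no | yes | no |

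Two things follow. In the pairs (3, 0.1) and (6, 0.1) the two cure definitions disagree. The pairs (1, 0.5) and (6, 0.1) meet both sets of 3.1 criteria. A stim-Tg below 2 with a conversion or rise in anti-Tg antibodies would also meet both. With stimulated values alone (below 2 for cure, 5 or more for suspected persistence) no Tg pair meets both.

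**Which endpoint is exposed.**

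- *3 months.* All participants are stimulated, the laboratory list names the stimulated value only, and Section 7 tests athyroglobulinemia. One loose end is that a remark in 3.3.1.3 about non-NIH sites follows a line naming both stim-Tg and the scan. The study calendar attaches its optional-site note to the scan row and leaves the 3-month stimulation entry unmarked, which supports reading stim-Tg as required.
- *1 year.* Some non-NIH patients may have no stim-Tg. The annual unstimulated value would then be the only one available, and the 3.1 wording accepts it.

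**Direction and size.** Let p be the cure rate on stim-Tg, and q the share of patients not cured on stim-Tg whose unstimulated Tg is 0.2 or less. If both values were available for everyone, the literal 3.1 rate would be p + (1 − p)q, which is never below p. If q were the same in both arms, the arm difference would become (1 − q) times its stim-Tg value. As an assumption only, q = 0.05, 0.10 or 0.20 would multiply the difference by 0.95, 0.90 or 0.80. The documents do not give q, its value by arm, or the proportion of non-NIH patients who will lack a 1-year stim-Tg.

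**The case against.** The strongest reply is that *or* has an ordinary meaning here: apply the limit that belongs to the test taken. Within either test the Tg limits do not collide (below 2 against 5 or more; at most 0.2 against above 0.3), and the overlaps in Tg values need both tests at about the same time. This reading removes most double classification. It does not remove the conflict at 1 year. Under it, cure at non-NIH sites is judged on an unstimulated value, although the objective names stim-Tg.

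Three stronger readings are tempting, and the documents do not support them.

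- **A reader might infer that the primary cure rate is inflated.** No planned analysis of the primary endpoint is shown to use the unstimulated limit. The objective, the 3-month laboratory list and Section 7 all point away from it.
- **A reader might infer that cure and persistence must divide the patients cleanly, with any sign of persistence overriding cure.** Section 3.1 says persistence is only suspected, raised Tg leads to work-up (Section 3.3.1.5), and the recurrence outcome in 1.1.2 needs biopsy or pathology proof. No analysis needs exclusive classes. An override would let an unstimulated value or an antibody change overrule the stimulated test that the objectives name, and Section 1.2.2.6 says antibody levels can fluctuate and can rise transiently after ablation.
- **A reader might take the size from Section 1.2.2.5.** That section says about 20% of patients with suppressed Tg below 1 ng/ml exceed 2 ng/ml when stimulated, and then: "In this patient population, one third will have identification of persistent or recurrent disease". Those patients were tested 12 months after surgery and radioiodine, under a limit five times the 0.2 ng/ml used here. The same section ends by crediting an unstimulated Tg of 0.1 ng/ml or less, on a highly sensitive assay, with very high negative predictive value against stim-Tg. The 20% is therefore not q.

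**Conclusion.** The point holds in a limited form. Section 3.1 conflicts with Sections 1.1 and 1.2.2.5 on what counts as biochemical cure. Read literally, it admits patients whose stim-Tg is not below 2 ng/ml, and it has no rule for discordant results. The primary 3-month rate is largely protected. The exposure is the 1-year secondary cure rate, where the test behind the word cure could differ by site.

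The size cannot be stated from the documents. If both values are available, the literal rule can only raise the rate, and under an equal q it shrinks the arm difference. That direction rests on the equal-q assumption. No sample-size or power figure is wrong on this account. The 5 ng/ml limit appears in Section 1.2.2.5 as "Stim-Tg >5 ng/ml or unstimulated Tg >0.3 ng/ml has been associated with persistent and recurrent disease" and in Section 3.1 as 5 or more. This affects only a value of exactly 5 and is editorial.

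**What to change.** Amend the paragraph after Table 2 in Section 3.1 so that it agrees with 1.1.1, 1.1.2 and 1.2.2.5, and add the matching derivation rule to Section 7:

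1. For the 3-month and 1-year cure endpoints, cure is derived from stim-Tg alone (below 2 ng/ml).
2. Results based on unstimulated Tg are reported separately and do not enter those rates.
3. Patients without a stim-Tg at 1 year are shown as not assessed for that endpoint, with counts by arm and by NIH or non-NIH site.
4. As an editorial matter, the two forms of the 5 ng/ml limit are made to agree.

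This concerns endpoint derivation only and leaves clinical use of the Tg and antibody limits as it stands. The cost is one paragraph and one derivation rule. Fewer non-NIH patients will count toward the 1-year rate, and that rate may be slightly lower than under the present wording.
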